However, GRASP does not include the component of affected UL daily functional use. Affected UL daily functional use is important because from clinical experience, stroke patients often confine the practice of their affected UL to just during therapy sessions, as most of them do not know how to use their affected UL after stroke, especially for those with lower UL motor function. Reduced affected UL use perpetuates even to chronic phase as they have not learned how to incorporate the use of their affected UL in daily life, resulting in the phenomenon of “learned non-use”.

In this new proposed program, ***Self-empowered Upper Limb Repetitive Engagement (SURE)*** program, specific instructions and guidance according to the level of their affected UL motor function will be given to guide and increase affected UL daily functional use in stroke patients in the ward. In addition, prescribed specific exercise according to the level of their affected UL motor function will also be given and guided to facilitate patients to exercise by themselves in the ward. The activity of the affected UL will be objectively and accurately monitored, reviewed and feedback to the patients to facilitate affected UL use and practice using accelerometers. Accelerometry has been found to be valid and reliable in the measurement of UL use in

stroke patients.

To date, there is no therapy program that has specifically and systematically been introduced in Singapore to facilitate UL practice and use of the stroke patients in the ward. Taking into consideration the challenge of increased UL practice during early post-stroke in the real clinical world, it is, therefore, important to investigate the feasibility and effectiveness of **SURE** program and the potential imaging biomarkers to optimize the neuro-rehab

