2.2. Primary Objectives

To investigate the effectiveness of SURE program to increase UL practice in the ward and improve UL functional outcomes after stroke. To correlate the imaging biomarkers with the neuro-recovery outcomes under SURE and controlled program.

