3. STUDY POPULATION

3.1. List the number of subjects to be enrolled.

20 subjects will be randomly assigned to a control (N=10) and experimental group (N=10). 4 normal healthy subjects will also be recruited for fMRI investigations.

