6. METHODS AND ASSESSMENTS

Outcome Measures

UL functional outcome measures

UL Fugl Meyer Scale (ULFM)

UL Fugl Meyer Scale will be used to stratify subjects to their level of UL severity and assessment of UL impairment. ULFM score can be subdivided into 3 categories to define the different level of severity of paresis (severe= 0 to 22; moderate=23 to 50; mild>= 51). ULFM will be one of the primary outcome measures to determine UL recovery.

Action Research Arm Test (ARAT)

ARAT will be used as the primary outcome measure of UL functional outcome. ARAT will be one of the primary outcome measures to determine UL recovery.

Measure of UL practice and use

Rating of Everyday Arm-use in the Community and Home (REACH Scale)

The REACH scale is a self-report measure that captures how much an individual with stroke use affected UL outside clinical setting. It has one scale for subjects whose dominant UL is affected and another scale for subjects whose non-dominant UL is affected. It will be used to rate patients' affected UL use after discharge.

Measure of UL practice and use using accelerometry

One tri-axial accelerometer (ActiGraph GT3X+, ActiGraph LLC, Pensacola, Florida) will be placed on subject's unaffected wrist to establish the duration of unaffected UL use in the ward for 3 days in the first week. Another tri-axial accelerometer will be placed on subject's affected wrist for 3 weekdays each week of the 4-week intervention period to assess the amount of affected UL use. The accelerometers will be worn by all subjects (both experimental and control groups) from 8am to 8 pm on the day of donning.

Measures of feasibility of accelerometry in measuring affected UL use

The compliance rate of wearing the accelerometers during the 4 weeks of intervention period will be used to assess compliance. Subjects will also be asked to fill a questionnaire to rate the acceptance, ease, comfort, discomfort, benefits, and problems of wearing the accelerometers in the ward.

*Measures of **SURE** program's feasibility*

The key measure of **SURE** program's feasibility will be the additional affected UL practice and use per day as measured by the accelerometers.

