11. SAMPLE SIZE AND STATISTICAL METHODS

11.1. Determination of Sample Size

Since this study is a pilot exploratory trial, results of individual subjects from each group will be analysed in

detail to determine the difference in brain neuroplasticity between the control and experimental groups. N=10 from each group is chosen because it is deemed feasible to recruit stroke patients who will be willing to participate in this study clinically in the period of 2 years (the time period of the funding).

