11.2. Statistical and Analytical Plans

a. Study Statistical Analysis

Statistical analysis will be performed using STATA version 10.0 for Windows (StataCorp, TX, USA). Descriptive statistics will be used to describe subjects' demographics in each group.

Analysis of UL Functional Outcome

Wilcoxon signed-ranked tests will be used at each time points (pre, 2 weeks after start of intervention, post, 1month post-intervention, 3months post-intervention) to compare UL functional outcomes between the experimental and control groups. The significance level for all statistical tests will be set at $p<0.05$ levels. All data will be analysed by intention to treat.

Analysis of feasibility of accelerometers to measure affected UL use

Analysis of the compliance rate and responses from the questionnaire will be used to determine the feasibility and acceptance of using accelerometers to measure affected UL use after stroke.

Analysis of SURE Program's feasibility

Wilcoxon signed-rank test will also be used to compare outcomes of pain, fatigue and spasticity pre-and post-intervention period. The differences in the duration of affected UL use per day and the ratio of affected UL use/ non-affected UL use between the experimental group and control group (from the accelerometer recordings), the rate of compliance, the proportion of subjects who successfully complete the whole training, and the dropout rate will be calculated to assess the feasibility of **SURE Program**.

Analysis of fMRI investigation

Comparison of activation in primary motor cortex, secondary motor cortex and cerebellar hemisphere for bilateral sides will be done by comparing mean percentage signal change (%SC), absolute voxel counts (VC) and changes in geometric centers of these areas on both sides¹⁷. In addition, a laterality index (LI) will also be calculated to determine the relative cortical activity. Asymmetry has been found to restore to normal (L=1.0) when the affected hand movement improved after rehabilitation⁴¹.

Analysis of resting state fMRI/DTI

Functional connectivity and tract integrity^{32,38} will be studied by FSL with the normalization method^{39,40}. The secondary degeneration of the brain in the remote region to the primary lesion will also be studied for the sub-groups of subjects with less motor recovery³⁰.

MRS analysis

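### Daily affected-arm use is planned as a between-group difference with no covariate, although pre-intervention ULFM is held on every patient and could sharpen the estimate at almost no cost

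*Protocol*

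**What the plan says.** - **Objective.** Protocol section 2.2: "To investigate the effectiveness of SURE program to increase UL practice in the ward and improve UL functional outcomes after stroke". A further sentence there adds the correlation of imaging biomarkers with recovery.
- **Measure.** Section 6 states that the key measure of the program's feasibility "will be the additional affected UL practice and use per day as measured by the accelerometers". Both groups wear the devices. The affected wrist is recorded on 3 weekdays in each of the 4 intervention weeks, so no pre-intervention value is scheduled for it. The same section names ULFM and ARAT as the primary outcome measures.
- **Analysis.** Section 11.2, under program feasibility, plans to calculate "The differences in the duration of affected UL use per day" between the two arms, and likewise for the use ratio of the two limbs. No covariate, model or test is attached to this measure.
- **Baseline severity.** ULFM of 50 or below is an entry criterion (section 3.3). ULFM is assessed before the intervention (section 5, where it is printed ULM) and sets the booklet level in the experimental arm.
- **Link between function and use.** Section 1.1 reports from clinical experience that most patients "do not know how to use their affected UL after stroke, especially for those with lower UL motor function".
- **Stratification.** Section 6 says ULFM will serve to stratify subjects by severity. Section 6.1 describes a web-generated sequence without strata, and section 11.2 does not use ULFM as a covariate.
- **Size.** Section 11.1: "N=10 from each group is chosen because it is deemed feasible to recruit stroke patients" within the funding period. No effect size, SD or power is given.

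**The concern.** Entry severity runs from ULFM 0 to 50. If it predicts daily arm use, as section 1.1 suggests, part of the spread in use within each arm comes from severity and not from the program. A plain group difference leaves that spread in the error term. With 10 per arm and no strata described in section 6.1, it also moves with whatever severity imbalance chance produces. The sample size is fixed by recruitment, so the analysis is the cheap place to gain precision. The outcome's own baseline is not available for the affected wrist, which makes ULFM the natural covariate. At stake is how precisely the trial can say how much practice the program adds.

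**Working it through.** The protocol states no power or effect size, so there is no figure to reproduce.

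**Inputs from the protocol:** n = 10 per arm (N = 20); significance level 0.05.

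**Assumptions:** two-sided test of t type (section 11.2 names none for this measure); true difference d = 1.0 within-arm SD of daily use; correlation r between pre-intervention ULFM and daily use of 0, 0.3, 0.5 or 0.7; linear relation with the same slope in both arms.

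**Unadjusted.** SE = sqrt(2/10) = 0.447 SD. Noncentrality = 1.0/0.447 = 2.24 with 18 df, giving power of 56%. The difference detectable with 80% power is 1.32 SD.

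**Adjusted for ULFM.** Variance factor V = (1 − r²) × (1 + 1/(N − 4)) = (1 − r²) × (1 + 1/16). SE = sqrt(0.2 × V), with 17 df. Equivalent unadjusted n per arm = 10/V.

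| r | V | SE (SD) | Power at 1.0 SD | Detectable at 80% (SD) | Equivalent n per arm |
|---|---|---|---|---|---|
| unadjusted | 1 | 0.447 | 56% | 1.32 | 10 |
| 0 | 1.0625 | 0.461 | 53% | 1.37 | 9.4 |
| 0.3 | 0.967 | 0.440 | 57% | 1.31 | 10.3 |
| 0.5 | 0.797 | 0.399 | 66% | 1.19 | 12.5 |
| 0.7 | 0.542 | 0.329 | 82% | 0.98 | 18.5 |

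A simulation with 8,000 runs per scenario agrees: adjusted power 54%, 58%, 65% and 81%.

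**Chance imbalance.** Without strata, the difference in mean ULFM between the arms has SD sqrt(2/10) = 0.447 of the ULFM SD. The probability that it exceeds 0.5 SD in either direction is 2 × (1 − Φ(0.5/0.447)) = 26%; for 0.75 SD it is 9%. An imbalance of 0.5 SD shifts the unadjusted difference by r × 0.5, which is 0.15, 0.25 or 0.35 SD at r = 0.3, 0.5 or 0.7. Adjustment removes this shift if the relation is linear.

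**Type I error.** With no true difference, the simulated rejection rate is 4.5% to 5.0% unadjusted and 4.5% to 5.2% adjusted.

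**The case against.** The strongest reply is that this is detail for a statistical analysis plan. Only the protocol is at hand, it never calls the difference unadjusted, and a later plan could add a covariate. That limits the point. Even so, section 11.2 does fix the quantity to be reported, and a better one can be had from data already collected.

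Several other limits stand:

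- The measure sits under feasibility in a pilot trial whose named primary outcomes are ULFM and ARAT. It would be too strong to call it half of the primary objective; practice is one of the effectiveness targets there.
- Section 1.1 gives a qualitative clinical observation. It does not report measured use by severity, and it describes patients without guidance. The program gives guidance by ULFM band, so the slope could differ between arms. With equal arms the coefficient would still estimate an average difference, but the gains above assume a common slope.
- Restricting entry to ULFM of 50 or below and MEP-positive patients may lower the correlation. At r = 0.3 the gain is negligible, and at r = 0 adjustment costs about 3 points of power.
- If the wording on stratification in section 6 refers to allocation, chance imbalance would be smaller than computed. Section 6.1 does not bear that reading out, but the protocol leaves it unclear.

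A reader might infer that the planned comparison is biased or prone to false positives. The documents do not support that: allocation is random, so the difference is unbiased on average and type I error stays near 5%.

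**Conclusion.** The point holds as a cheap improvement. Section 11.2 plans a valid but less precise estimate of added arm use than the data allow. For a 1.0 SD effect, adjustment moves power from 56% to between 53% and 82% as the assumed correlation goes from 0 to 0.7. It becomes material at about 0.5, where it is worth 12.5 unadjusted patients per arm instead of 10. The same reasoning applies to the use ratio, with its own unknown correlation: the ratio scales for general activity but does not account for entry severity. The power figures rest on an assumed correlation, effect size and test, and serve to illustrate precision. The conclusion does not depend on a significance test being run, because the narrower standard error carries directly into the confidence interval.

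**What to change.** In section 11.2, state that the group difference in each subject's mean daily affected-arm use, and in the use ratio, will be estimated from a linear model with arm and continuous pre-intervention ULFM, with a 95% confidence interval, and that the unadjusted difference will be shown beside it. Fix the scale of analysis in advance; do not leave a transformation to be chosen after the data are seen. Say also whether the stratification by ULFM in section 6 refers to allocation, analysis or description, so that it agrees with sections 6.1 and 11.2.

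The cost is a sentence or two and no new data. The statistical price is one degree of freedom, a linear common-slope assumption with 20 subjects, and about 3 points of power if ULFM turns out to be unrelated to use. Naming the covariate beforehand also removes the temptation to choose one after an imbalance is seen.

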2. HYPOTHESIS AND OBJECTIVES

2.1. Hypothesis

1. **SURE** program increases UL practice in the ward and improves UL functional outcomes post-stroke
2. Increased UL practice early post-stroke period influences neuroplasticity positively to optimize UL recovery
3. Imaging biomarkers are associated with rehab-methods and recovery of UL post-stroke

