The subjects will be asked to perform the exercises 60 minutes (3x 10- 20 minutes) distributed across morning, afternoon, and evening per day for 6 days per week during the 4-week intervention period. They will also be asked to perform the functional tasks as and when is required for their daily function for 6 days per week during the 4-week intervention period. The subjects will be given an Exercise Log to tick and track number of repetitions of the exercises and functional activities each day, the number of days the protocol is completed, and the level of fatigue and pain experienced. If the subject is discharged from the hospital before the 4 weeks of intervention period, he/ she has to carry on with the protocol till the intervention period ends. The CPI will continue to review exercises and the amount of affected UL use with the subjects at home if the subjects are discharged till the intervention period ends.

Control Group

The control group will receive an education booklet with 10 modules. The education booklet will contain information on stroke, recovery and management strategies after stroke. Subjects are to complete 2-3 modules per week and answer 1-2 simple questions after each module. Each module including answering questions takes approximately 5-10 minutes to complete. The CPI will review the information with the subjects 3 times per week for the first 2 weeks, two times for the third week and one time for the fourth week of intervention period.

Both groups will continue with their daily routine therapy sessions in the hospital. The treating therapists will record the duration of therapy of each subject per day.

UL functional outcome measures- ULM and ARAT will be assessed pre-intervention, 2 weeks after start of intervention, post-intervention, 1month and 3months post-intervention. Measures of **SURE** program's feasibility such as VAS pain score, fatigue level, and MAS of biceps and finger flexors will be measured pre-intervention, 2 weeks after start of intervention and post-intervention. A team member who is blinded to which group the subjects are in will perform the outcome measure assessments.

Multimodal imaging for the normal healthy control will be performed once to establish the activation pattern in normal. Multimodal imaging assessment for the patient subjects will be done pre-intervention, post-intervention, and 3months post-intervention.

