Multimodal MRI data (T1, T2-flair, PCASL, DTI, MRS, resting-state fMRI and task-based fMRI) will be collected immediately pre-, post-, and 3months post treatment using a 3T Siemens MR system at the Clinical Imaging Research Centre using a 32 channel receive array head coil. Measurements will be made to assess changes in brain structure, metabolic status and connectivity as follows:

For anatomical delineation of the stroke lesion, and for normalization of functional data, a T1 weighted MPRAGE image (1mm³ isotropic voxels, 176 sagittal slices, TI/TE/TR=900/3/1950ms) and a T2 weighted FLAIR image (1x0.5x2mm, TI/TE/TR= 2500/78/2500ms) will be acquired.

To investigate changes in metabolic status of the tissue, a pseudo-continuous arterial spin labelled acquisition (PCASL) will be used to assess brain perfusion (3mm isotropic voxels). In addition, magnetic resonance spectroscopy will be used to measure concentrations of gamma-amino butyric acid (GABA, the main inhibitory neurotransmitter) and Glx (glutamate plus glutamine concentrations, the main excitatory neurotransmitter and its cycling intermediate) from a MEGA-PRESS localized volume in primary motor cortex (2x2x2cm volume)

For assessment of changes in neuronal connectivity, Diffusion Tensor Images (68 directions, b=1000, TE/TR=98/9100ms, plus 6 b=0 scans, 2mm isotropic voxels) will be collected to assess changes in fractional anisotropy related to structural connectivity. To investigate changes in functional connectivity, resting state connectivity data will be collected, as well as assessing changes in activation induced fMRI BOLD responses during an elbow extension task.

fMRI Activation paradigm

Subjects will be asked to extend their elbow to push against a bulb distally in a self-directed comfortable pace on a wooden/plastic board secured on their abdomen during fMRI investigation. All subjects will practice outside the scanner to reduce the mirror movements from the unaffected UL. For the task based acquisition, 12s of active task will be followed by 16s of resting (to allow the hemodynamic response to return to baseline). This will be repeated 9 times.

Neuroplasticity Investigation

fMRI imaging and image Analysis

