A one-way ANOVA test will be performed to assess differences across the visits (pre, post, and 3months post intervention). Provided a significant difference is found, a paired t-test will be used. Due to an abundance of measurable metabolites, metabolite analysis will be limited to those defined by our hypothesis (changes in GABA and Glx) to minimise multiple comparisons.

b. Safety Analysis

Safety analysis will be done by monitoring the adverse events and complaints of the study daily.

c. Interim Analysis

Interim analysis of the data and study's safety and complaints will be performed every quarterly. If the analysis of study's safety shows that the subjects' safety is compromised because of the study procedures, the study will stop.

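### The tests fixed for GABA and Glx compare visits only, so none compares SURE with control, although the trial sets out to determine that difference

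*Protocol*

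**What the plan says.** The MRS paragraph of Protocol section 11.2 fixes two tests. The first: "A one-way ANOVA test will be performed to assess differences across the visits (pre, post, and 3months post intervention". The second depends on the first: "Provided a significant difference is found, a paired t-test will be used". The outcomes are narrowed on purpose: "metabolite analysis will be limited to those defined by our hypothesis (changes in GABA and Glx) to minimise multiple comparisons". The paragraph does not say whether the arms are pooled or analysed separately. Section 6 covers MRS acquisition and quantification and gives no group comparison.

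The aims that bear on this are set elsewhere:

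- Section 11.1 says individual results from each group will be examined "to determine the difference in brain neuroplasticity between the control and experimental groups".
- Hypothesis 3 in section 2.1 reads "Imaging biomarkers are associated with rehab-methods and recovery of UL post-stroke".
- Section 1.2(d) gives SURE's influence on neuroplasticity as one of the questions for which a randomised controlled design was chosen.
- Section 6 lists MRS in the multimodal imaging set, and section 5 schedules that set in patients of both arms: "Multimodal imaging assessment for the patient subjects will be done pre-intervention, post-intervention, and 3months post-intervention".

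**The concern.** A one-way ANOVA whose factor is visit asks whether the metabolite level changes over time. A paired t-test asks the same of two visits. Neither asks whether the change differs between SURE and control, so the randomised control arm is not used.

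Patients are enrolled within about three weeks of a stroke, and section 1.1 itself refers to spontaneous recovery in this period. If GABA or Glx drift in both arms, the visit test can be significant when SURE does nothing. That result could then be read as a SURE effect on neuroplasticity with no arm comparison behind it. In the other direction, a real change confined to SURE is diluted by the control arm in a pooled visit test, and the gate may stop any follow-up.

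**Working it through.** **Step 1: what each test contrasts.** The ANOVA has one factor, visit, with three levels. The paired t-test is within patient. Two readings are possible:

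- *Arms pooled:* the test addresses the average change over 20 patients. Arm does not appear.
- *Arms separate:* there are two within-arm p-values. One being below 0.05 and the other above is not a test of the difference between arms.

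Neither reading gives the contrast named in section 11.1. For comparison, section 11.2 does name both groups for UL function and for accelerometry, so the absence is specific to the MRS text.

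**Step 2: inputs for sizing.** From the documents: 10 patients per arm (section 3.1), three imaging visits, and significance level 0.05 (section 11.2; two-sided assumed). There is no planned figure to reproduce, because section 11.1 bases the sample size on feasibility. Assumed, because the protocol gives nothing: SD 1 at each visit, equal correlation rho of 0.3 to 0.8 between visits, and visit means (0, d, d). Simulation, 40,000 trials per cell. The visit test is shown both literally (ordinary one-way ANOVA) and in repeated-measures form, which the paired follow-up suggests. The arm comparison is an ANCOVA at the post visit: outcome = arm + pre-intervention value.

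**Step 3: results.**

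| Scenario | Quantity | Literal ANOVA | Repeated-measures ANOVA | ANCOVA on arm |
|---|---|---|---|---|
| Both arms change 0.8 SD, no SURE effect | significant, arms pooled | 74-79% | 86-100% | about 5% |
| SURE alone changes 0.8 SD | significant, arms pooled | 3-13% | 27-70% | 40-78% |
| Both arms change 0.5 SD, tests run per arm | exactly one arm significant | 7-21% | 35-50% | not applicable |
| Same | SURE alone significant | 4-11% | 18-25% | not applicable |

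The pooled visit test is significant far more often when SURE has no effect (first row) than when only SURE changes (second row). It responds to shared change, not to the arm difference.

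**Step 4: what the arm comparison can deliver.** The expected 95% CI half-width for the arm difference is 0.91 SD at rho 0.3 and 0.57 SD at rho 0.8. Power for a SURE-only change:

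| Change in SURE only | at 0.05 | at 0.0125 |
|---|---|---|
| 0.8 SD | 40-78% | 20-55% |
| 0.5 SD | 19-40% | 7-20% |

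Two metabolites at two follow-up visits make four tests. With independent tests the familywise error would be 1 − 0.95^4 = 18.5% at 0.05 each, and 1 − 0.9875^4 = 4.9% at 0.0125 each. Simulated with correlated visits it is 17.7-18.4% and 4.9-5.0%.

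**The case against.** The strongest reply is that the MRS component may never have been meant to compare arms. Section 6 introduces the metabolic measurements with "To investigate changes in metabolic status of the tissue", and section 11.2 speaks of changes in GABA and Glx; a visit test fits both. The background names corticospinal-tract FA and resting-state fMRI as candidate biomarkers, not GABA or Glx. Section 5.1 assigns the neuroplasticity question to the fMRI investigations, and the list of modalities for longitudinal analysis in section 6 omits MRS. The objective "To correlate the imaging biomarkers with the neuro-recovery outcomes under SURE and controlled program" could be met by correlations within each program. These points stand in part: the link from MRS to the arm comparison is inferred, and that objective is weak support. But section 11.1 speaks of neuroplasticity in general, and MRS is in the imaging set collected in both arms.

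Section 11.1 also permits a descriptive, patient-by-patient comparison of the groups. That is true, but it supplies no between-arm estimate or test for GABA or Glx.

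A statistical analysis plan might add an arm contrast. That argument does cover the fMRI and resting-state/DTI paragraphs, which name no significance test, and the point is not raised against them. For MRS the protocol has chosen the tests and made one conditional on the other.

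Last, the repeated-measures figures overstate the problem if the ANOVA is taken literally. That is correct for false signals: the per-arm figure falls from 35-50% to 7-21%. The literal test still confuses shared change with a SURE effect, and it makes the gate worse.

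**Conclusion.** The concern holds. The tests stated for GABA and Glx answer whether levels change over visits and cannot support a conclusion about SURE against control. That follows from the wording and needs no simulation. The percentages illustrate the size under assumed SDs, correlations and shifts. In particular, the protocol does not say that GABA or Glx change in both arms. Nor does it say that a visit effect would be reported as a SURE effect; that is a risk the wording leaves open.

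Importance is moderate. MRS is exploratory and the trial is a pilot. Section 6 makes ULFM and ARAT the primary outcome measures, and their comparison does not depend on this paragraph. What is at stake is the neuroplasticity conclusion drawn from MRS. It should be fixed.

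**What to change.** In the MRS paragraph of section 11.2, make the arm difference the stated contrast for GABA and for Glx. Either of two forms will do:

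- an ANCOVA at post and at 3 months, with arm and the pre-intervention value as terms; or
- a mixed model with patient as a random effect and arm, visit and arm-by-visit as fixed effects.

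Report each arm difference with its 95% CI, label it exploratory, and do not make it conditional on the visit ANOVA. Keep within-arm changes over visits as description; if a visit test is retained, put it in repeated-measures form.

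The cost is analysis wording only, because the scans are already scheduled in both arms. The price is low precision, which the text should admit: estimates and intervals, not p-values, should carry the conclusion. The exploratory label must go in with the change, because four tests at 0.05 carry about 18% familywise error. If significance is to be claimed, 0.0125 per test holds that error near 5%, at the lower power shown in step 4.

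### Section 11.2 gates the GABA and Glx analysis on a one-way ANOVA across three scans of the same patients; run as named, the gate is conservative and loses power

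*Protocol*

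**What the plan says.** The MRS paragraph of Protocol section 11.2 sets out two steps. The first is the omnibus test: "A one-way ANOVA test will be performed to assess differences across the visits (pre, post, and 3months post intervention". The second depends on the first: "Provided a significant difference is found, a paired t-test will be used". The scope is narrow: "metabolite analysis will be limited to those defined by our hypothesis (changes in GABA and Glx) to minimise multiple comparisons". The level comes from the same section: "The significance level for all statistical tests will be set at $p<0.05$ levels".

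The design makes the visits repeated measures. Section 5 states: "Multimodal imaging assessment for the patient subjects will be done pre-intervention, post-intervention, and 3months post-intervention". Section 6 confirms that spectroscopy is part of each session: "Multimodal MRI data (T1, T2-flair, PCASL, DTI, MRS, resting-state fMRI and task-based fMRI) will be collected immediately pre-, post-, and 3months post treatment".

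The protocol names no subject factor, repeated-measures form or mixed model for this analysis. It does not say whether the test is run within each arm of 10 or on all 20 patients. It gives no standard deviation, within-subject correlation or expected change for GABA or Glx. Section 11.1 bases the sample size on recruitment feasibility.

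**The concern.** Unqualified, a one-way ANOVA is the test for independent groups. Here the three groups would be the same people scanned three times. Stable differences between patients then stay in the error term, although they cancel from the comparison of visit means. The second step, a paired t-test, removes those differences. So the two steps rest on different error structures, and the more efficient one is reached only through the less efficient one.

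GABA and Glx are the only metabolites to be tested, and they serve the secondary neuroplasticity objective in section 2.3. With a sample this small, most of the information about change lies in the within-patient comparison. A gate that ignores it can stop a real change before the paired test is run.

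**Working it through.** The protocol states no power or effect size for this analysis, so there is no figure to reproduce.

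**Inputs from the protocol:** three visits; the same patients at each; n = 10 per arm or 20 pooled (section 3.1); level 0.05 (section 11.2).

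**Assumptions:** normal data; equal variance σ² = 1 at each visit; equal correlation ρ between any two visits, taken as 0.3, 0.5 and 0.7; a change of d SD present at both post-baseline visits; two-sided paired t-test.

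**Error terms.** Write each value as visit mean + subject effect (variance ρσ²) + residual (variance (1 − ρ)σ²).

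- Expected visit mean square = (1 − ρ)σ² + n Σ(μⱼ − μ̄)²/2
- Expected error mean square, one-way ANOVA = σ²
- Expected error mean square, repeated-measures ANOVA = (1 − ρ)σ²

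With no true change, the one-way ratio is centred near (1 − ρ) instead of 1. For n = 20 the one-way critical value is F(2, 57) = 3.16. On the scale of a correctly formed F, the gate therefore demands about 3.16/(1 − ρ): 4.5, 6.3 and 10.5 at ρ = 0.3, 0.5 and 0.7.

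**True type I error of the one-way gate (simulation, nominal 5%):**

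| ρ | n = 10 | n = 20 |
|---|---|---|
| 0 | about 5% | about 5% |
| 0.3 | 1.7% | 1.5% |
| 0.5 | 0.6% | 0.4% |
| 0.7 | 0.1% | 0.03–0.05% |

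A repeated-measures F stays at about 5% throughout.

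**Power, n = 20, d = 0.5.** The visit means are 0, 0.5, 0.5, with mean 1/3, so Σ(μⱼ − μ̄)² = 1/9 + 2 × 1/36 = 0.167. The repeated-measures F has noncentrality 20 × 0.167/(1 − ρ) = 4.76, 6.67 and 11.11, with critical value F(2, 38) = 3.24. This gives power of 45, 60 and 83%. Simulation agrees to within about one percentage point, and the same simulation gives the one-way gate.

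| ρ | One-way gate | Repeated-measures F | Significant pre–post paired tests stopped by the gate |
|---|---|---|---|
| 0.3 | 28% | 45% | 45% |
| 0.5 | 23% | 60% | 62% |
| 0.7 | 18% | 83% | 78% |

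**Sensitivity: share of significant pre–post paired tests stopped by the gate, ρ = 0.3 / 0.5 / 0.7:**

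| Change | n = 10 | n = 20 |
|---|---|---|
| 0.5 SD | 59 / 76 / 89% | 45 / 62 / 78% |
| 0.8 SD | 39 / 52 / 66% | 15 / 20 / 22% |
| 1.0 SD | 24 / 34 / 41% | 5 / 5 / 3% |

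If the change is instead sized so that the ungated paired test has 80% power, the gate stops 14–18% of significant paired tests at ρ = 0.3, 34–39% at 0.5 and 68–76% at 0.7 (n = 10 and n = 20 respectively).

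**Effect of correcting the gate.** For that same 80% effect, a repeated-measures gate has power of about 0.84–0.86. The chance of passing both the gate and the paired test is about 0.76–0.77 at every ρ, against 0.80 with no gate.

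**The case against.** The strongest reply is that one-way may simply mean one factor, visit. A one-way repeated-measures ANOVA fits that description, and the paired follow-up suggests the authors knew the scans were paired. The protocol never says that the visits are treated as independent groups. This reading is fair and cannot be excluded. It does not remove the need for a change: without a qualifier the term names the independent-groups test, and an analyst following the text literally would run it. Because the protocol itself fixes the test and the gating rule, this is more than a detail left to a later plan.

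Three stronger readings are tempting, and the documents support none of them.

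- *Most real change would be screened out.* This needs a correlation and an effect size that the protocol does not give. The share stopped runs from 3% to 89% in the sensitivity table above.
- *A failed gate would be reported as no metabolic plasticity.* The protocol contains no such rule, and section 11.1 describes a pilot in which individual results are examined in detail.
- *The gate itself is the fault and must go.* A correctly specified omnibus test holds about 5% and costs little power. Keeping one is consistent with the stated aim of limiting multiple comparisons.

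The 20-patient figures also assume pooled arms with the same change in both. The protocol does not state this, and it fits poorly with the hypothesis that extra practice alters neuroplasticity. They illustrate the mechanism and are not forecasts for this trial.

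**Conclusion.** The test is wrong as written. Applied literally to three scans of the same patients, it uses the wrong error term and disagrees with the paired test that it controls. That the gate is conservative whenever the within-subject correlation is positive follows from the design. The size does not: under the stated assumptions, with 20 pooled patients and a 0.5 SD change, power falls by about 17 points at ρ = 0.3 (45 − 28), 37 at 0.5 (60 − 23) and 65 at 0.7 (83 − 18). At ρ = 0 nothing is lost, and for a 1.0 SD change in 20 patients the gate stops only 3–5% of significant paired tests. Losses are larger if the test is run in one arm of 10.

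The error costs power and does not raise the false-positive rate. It is confined to the secondary, exploratory MRS analysis. The clinical primary outcome measures, ULFM and ARAT, are unaffected. The wording should be corrected, but the trial's main clinical conclusions do not depend on it.

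**What to change.** In the MRS paragraph of section 11.2, replace the one-way ANOVA with either of the following, fitted separately for GABA and for Glx:

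- a repeated-measures ANOVA with visit as the within-subject factor; or
- a mixed model with visit as a fixed effect and a random subject intercept, using all available scans. This also keeps patients who miss a visit.

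Report the post-minus-pre and 3-month-minus-pre contrasts with 95% confidence intervals, whether or not the omnibus test is significant. The omnibus test may stay as the gate for claiming significance. State whether the analysis is per arm or pooled.

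If a repeated-measures ANOVA was always meant, adding those words to the sentence is enough to correct the gate. The cost is one sentence and a few lines of code, with no new data, visits or patients.
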